### **18. Provisions to Protect the Privacy Interests of Participants**

*18.1. Protecting Privacy:* Participant privacy will be protected by removing any identifiable information from the research data

*18.2. Access to Participants:* The research team is permitted to access private information about participants if they are patients of record at the University of Minnesota School of Dentistry. This information may be needed to determine if any treatment or medication precautions need to be followed to safely treat the participant.

### **19. Compensation for Research-Related Injury**

*19.1. Compensation for Research-Related Injury:* Compensation for Research-Related Injury: In the event that this research activity results in an injury, treatment will be available, including first aid, emergency treatment and follow-up care as needed. Care for such injuries will be billed in the ordinary manner to you or your insurance company. If you think that you have suffered a research related injury, let the study doctors know right away.

## **20. Consent Process**

### **20.1. Consent Process (when consent will be obtained):**

- Consent will take place during the consultation appointment, after the research participation offer has been extended.
- If the potential participant needs time to consider the research invitation, a time period of half the time until their treatment initiation appointment will be given for the participant to consider the offer. This time frame allows the participant to make an informed decision and allows the clinic staff time to schedule and plan treatment with the Gentlewave system should it be necessary.
- It will be the duty of the treating clinician to make sure the participant understands the information provided.

### **20.2. Waiver or Alteration of Consent Process (when consent will not be obtained): N/A**

### **20.3. Non-English speaking Participants:**

- The University of Minnesota School of Dentistry Graduate Endodontics clinic sees a diverse population of patients whom speak a variety of languages other than English. Oral information will be provided through the use of an interpreter, and written information will be provided once it is determined which specific language translations are needed.
- Interpreters are required by the University of Minnesota to be present for any patient interaction for patients who do not speak English. If a patient qualifies for recruitment, the interpreter will be available at the time of consult and recruitment to present the research opportunity and obtain consent. HRP-507 Short form for consent will be used. The interpreter is also required to be present during any treatment and follow-up visits as well.

### **20.4. Participants Who Are Not Yet Adults (infants, children, teenagers under 18 years of age):**

- Only adults ages 18 years or older will be recruited for research participation

### **20.5. Adults Unable to Consent:**

- Adults unable to consent will not be recruited for the study.

## **21. Setting**

### **21.1. The site of the research will be the University of Minnesota School of Dentistry Graduate Endodontics clinic. Research procedures will be**

performed by resident dentists who will be overseen by certified endodontists on faculty at the school of dentistry.

21.2. International Research: N/A

## 22. Multi-Site Research

N/A

## 23. Resources Available

23.1. Resources Available:

- The study will be conducted by a student investigator and co-residents, the faculty advisor will be available for assistance should there be any needed. There are also faculty clinicians trained on the usage of the Gentlewave device should any issues arise.
- Patient consultations for treatment occur daily, either through normal treatment scheduling, or through emergency scheduling. These patient pools should contain more than a sufficient number of necessary participants.
- The research treatment, data collection, and data analysis should require no more than 12-15 months.
- The facilities include 9 dental operatories and a surgical suite equipped with all necessary equipment and instruments to perform standard root canal treatment, including dental operating microscopes. There is one Gentlewave machine, with necessary treatment fluids and hand pieces for all research patient cases.
- Should participants have a medical emergency, we have a first aid kit, ambu bag, oxygen, and AED available. As well as a nearby hospital and fast access to emergency responders.
- All Graduate endodontics faculty, residents, and assistants have been trained on how to properly operate and troubleshoot the Gentlewave device. Prior to starting the research, each participating resident will be given verbal and written instruction on the consent process, the protocol for conducting treatment, and which information needs to be collected from each participant.

## **Research Design**

This study was a single-blind, randomized, controlled clinical trial comparing the incidence and severity of postoperative pain and mechanical allodynia following root canal treatment. Based on a similar previous study (81), a sample size of 38 patients (19 per group) was necessary to achieve a power of 80%. Following a standard endodontic cleaning and shaping protocol, the independent variables are (1) conventional side-vented needles for irrigant delivery combined with ultrasonic activation and (2) irrigation using the Gentlewave system. Five 2nd year residents in the Graduate Endodontics division at the University of Minnesota School of Dentistry performed all treatments. The target population of the study included patients of the Graduate Endodontics clinic requiring root canal treatment.

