### **Inclusion criteria were:**

- (i) Patients who are 18 years of age or older
- (ii) Patients with premolar or molar with a pulpal diagnosis of necrotic pulp, symptomatic irreversible pulpitis, asymptomatic irreversible pulpitis and a periapical diagnosis designated as symptomatic including symptomatic apical periodontitis, chronic apical abscess, acute apical abscess requiring root canal therapy.
- (iii) teeth with fully formed apices
- (iv) teeth without internal or external resorption.

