### **Exclusion criteria were:**

- (i) patients under the age of 18 or those incapable of giving informed consent
- (ii) Patient with premolar or molar with a pulpal diagnosis of normal pulp, previously treated, previously initiated and a periapical diagnosis of asymptomatic apical periodontitis or normal apical tissue requiring root canal therapy.
- (iii) teeth with immature apices

- (iv) teeth with apices in the maxillary sinus or those teeth where the apical lesion has eroded the bone of the maxillary sinus floor.
- (v) teeth with internal or external resorption,
- (vi) teeth with carious lesions or deficient crowns that cannot be repaired before accessing the pulp chamber.

Prior to treatment, a diagnostic exam and sensibility testing were performed. Pain data was collected at the time of presentation by having patients indicate their peak pain or discomfort level at the six-hour mark prior to root canal treatment and symptomatic apical periodontitis was confirmed by using percussion testing and a modified occlusal force meter (Occlusal Force-Meter, GM10, Nagaro Keiki, Tokyo, Japan), as demonstrated by Khan (75). The occlusal force meter numerical reading was recorded at maximal bite force prior to feeling pain on the symptomatic tooth and maximal bite force on the contralateral tooth. Pain measurements were made using a 0-100 NRS. The '0' mark represented 'no pain' and the '100' mark represented 'the worst pain imaginable'. There were 39 additional numeric markings between the '0' and '100' marks that patients could choose, and patients were instructed to write in their pain rating if it was not sufficiently represented on the scale. Along with the numeric scale, the surveys included Wong-Baker FACES as well as verbal markers indicating low, mild, moderate, high, and very high pain. For this study, scores in the very high range were considered severe pain. Scores 0-19 represented low pain, 20-39 was mild pain, 40-59 was moderate pain, 60-79 was high pain, and 80-100 was very high or severe pain.

Patients were divided into one of two treatment groups. Each treatment was scheduled for two appointments regardless of experimental group. For both groups, following confirmation of profound anesthesia, a rubber dam was placed in order to isolate the tooth in treatment. Prior to

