accessing the pulp chamber, all caries, defective restorations, and deficient crowns were removed. A pre-endodontic build-up was placed if necessary, to maintain isolation. Straight-line access to the pulp orifices was then achieved. Hand files and an electric apex locator were used to determine the working length which was then verified with a periapical radiograph.

For the control (standard endodontic treatment) group, during the initial appointment the following were accomplished: Clinical exam, pre-endodontic build-up (if necessary), working length determination, all canals were instrumented using hand and rotary files to a minimum size and taper of at least 25/04 to within  $\frac{1}{2}$  to 1 mm short of the apical terminus. Between each file, 5.25% NaOCl was used to disinfect the canals and flush debris. Following instrumentation, NaOCl was ultrasonically activated for 30 seconds in each canal. Canals were then dried; UltraCal XS (Ultradent Products, Inc., South Jordan, UT) was placed into each canal measured 2mm short of working length. A spacer of either sterile cotton pellet or sterile sponge were placed followed by an interim restoration of either Cavit or Glass ionomer to a minimum thickness of 3.5mm.

In the experimental group during the initial appointment the following were accomplished: Clinical exam, pre-endodontic build-up (if necessary), working length determination, all canals were instrumented using hand and rotary files to a maximum size and taper of 20/07 to 1 mm short of the apical terminus. Between each file, 5.25% NaOCl was used to disinfect the canals and flush debris. Following instrumentation of the canals, Kool-dam heatless liquid dam was used to build an occlusal platform that functioned to support the GWS handpiece and seal the access opening during treatment. For molars, included gauges were used to determine the proper handpiece attachment. The GWS handpiece was positioned on the tooth for the entirety of the GWS treatment, which varied in length of time depending on the pulpal diagnosis of the tooth. The canals were then dried using paper points and UltraCal XS (Ultradent Products, Inc., South

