Jordan, UT) was placed into each canal measured 2mm short of working length. A spacer of either sterile cotton pellet or sterile sponge were placed followed by an interim restoration of either Cavit or Glass ionomer to a minimum thickness of 3.5mm. Once the temporary restoration was completed, patients were given the same 0-100 NRS pain assessment to take home and were asked to record their level of pain at 6, 24, 72, and 168 hours post-treatment. In order to control any pain that may have been unbearable, patients were educated on the ibuprofen and acetaminophen regimen introduced by Menhinick et al 2004 (92) and instructed to record how much was taken.

Patients then returned for a second appointment 2-4 weeks after the initial visit. Pain data was collected at the time of presentation by having patients indicate their peak pain or discomfort level at the six-hour mark prior to the appointment. The occlusal force meter numerical reading was recorded at maximal bite force prior to feeling pain on the symptomatic tooth and maximal bite force on the contralateral tooth. Pain measurements were made using a 0-100 NRS-41. Patients were anesthetized, teeth isolated with rubber dam, access was re-established by removing the interim restorative material and intracanal medicament. The appropriate final canal size was determined by the treating clinician and between each file, 5.25% NaOCl was used to continue to disinfect the canals and flush debris. Following instrumentation, NaOCl was ultrasonically activated for 30 seconds in each canal, each canal was then flushed with 17% EDTA for 1 minute followed by a rinse of 5.25% NaOCl. A final rinse of 95% ethanol was used for all sealers except for those made of bioceramic materials. Canals were then dried and filled with gutta-percha and the clinician's sealer of choice. In order to control any pain that may have been unbearable, patients were educated on the ibuprofen and acetaminophen regimen introduced by Menhinick et al 2004 and instructed to record how much was taken.

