### **Statistical Method**

NRS pain scores were compared between treatment groups at each post-operation time point (6, 24, 72, 168 hours) using linear mixed-effects models with fixed effects for treatment, time, treatment-by-time interaction, and pre-operation NRS pain score, and a random effect for participant to account for within-participant correlation of longitudinal measurements.

Categorical NRS pain scores were compared using mixed-effects logistic regression models with fixed effects for treatment, time, treatment-by-time interaction, and pre-operation NRS pain score category, and a random effect for participant. Mechanical allodynia bite force was compared between treatment groups using the two sample t-test. Mechanical allodynia bite force was compared between treated and control teeth within each treatment group, and between visit 1 and visit 2 in treated teeth within each treatment group, using the paired t-test. Age category, sex, pulpal diagnosis, tooth type, and visit 2 NRS pain category were compared between groups using the chi-square test for association. Continuous measures are summarized using means with 95% confidence intervals. Categorical measures are summarized using rates. Analyses were conducted using R version 4.0.3.

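### The SAP's aim on incidence and severity of mechanical allodynia after root canal treatment goes beyond the two bite-force readings, which support only a comparison of pain threshold 2-4 weeks after the first treatment visit, before the canals are filled

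*SAP*

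**What the plan says.** The SAP's Research Design section gives the purpose as "comparing the incidence and severity of postoperative pain and mechanical allodynia following root canal treatment".

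The assessments are described in the text after the SAP's exclusion criteria. Before treatment, "symptomatic apical periodontitis was confirmed by using percussion testing and a modified occlusal force meter". At that visit, "The occlusal force meter numerical reading was recorded at maximal bite force prior to feeling pain on the symptomatic tooth", with a further reading on the contralateral tooth. The randomised irrigation follows at the same visit; in the experimental arm, "The GWS handpiece was positioned on the tooth for the entirety of the GWS treatment".

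"Patients then returned for a second appointment 2-4 weeks after the initial visit". At presentation the pain score and both bite-force readings are repeated. The text then moves to anaesthesia, re-access, further filing and irrigation, and ends with "Canals were then dried and filled with gutta-percha". No later bite-force reading is described.

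Under Statistical Method, "Mechanical allodynia bite force was compared between treatment groups using the two sample t-test". Paired t-tests within each arm compare treated with control teeth, and visit 1 with visit 2 in treated teeth.

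The protocol adds little. Section 5.2 records bite force before treatment only, and sections 3.1 and 3.2 list no allodynia outcome.

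**The concern.** Read naturally, the aim promises a rate of allodynia, arising or present after root canal treatment, compared between arms. Three features of the plan work against that.

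- Pain on biting is part of how the symptomatic diagnosis is confirmed, so few if any teeth are likely to be free of it at entry and able to become new cases.
- The one follow-up reading falls between the two treatment sessions. It is too late for the acute period covered by the pain diary and too early for the period after the canals are filled.
- No rule classifies a tooth as having allodynia or not, and no proportion is analysed.

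At stake is what may be concluded. A report that follows the stated aim could claim an effect on the incidence of allodynia after root canal treatment that these readings cannot support. The comparison that they do support is left loosely specified, because its visit is not named.

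**Working it through.** No figure in the plan is in dispute. The check sets the bite-force readings against the treatment steps, then against the listed analyses.

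**Order of events (SAP, text after the exclusion criteria)**

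| Step | Time | Bite force read? |
|---|---|---|
| Diagnostic examination, before treatment | Visit 1 | Yes, treated and contralateral tooth |
| Instrumentation and randomised irrigation | Visit 1 | No |
| Pain diary | 6, 24, 72 and 168 h | No |
| Presentation, before anaesthesia | Visit 2, 2-4 weeks | Yes, treated and contralateral tooth |
| Further filing, irrigation and filling | Visit 2 | No |
| After completed treatment | After visit 2 | No |

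Readings after the randomised irrigation: 1. Readings within 168 h of it: 0. Readings after filling: 0.

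In hours, the follow-up reading falls between 2 × 7 × 24 = 336 and 4 × 7 × 24 = 672. Even the earliest is 336 − 168 = 168 h after the last diary point.

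**What each reading can show**

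- New onset needs teeth that are free of allodynia at the first reading. The force meter is used there to confirm symptomatic status, and the exclusion criteria rule out asymptomatic apical periodontitis and normal apical tissue. Few or no teeth should be at risk.
- The visit 2 reading follows the irrigation that differs between arms, and one common regimen is described for visit 2. It is therefore a legitimate post-randomisation outcome for the first session.
- It says nothing about the effect of visit 2 itself.

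**What the listed analyses estimate**

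1. Between arms, two-sample t-test: a difference in mean force, visit not stated. At visit 1 this would be a baseline comparison; at visit 2 it would be the treatment comparison, unadjusted for baseline.
2. Within arm, treated against control tooth: not a comparison of arms.
3. Within arm, visit 1 against visit 2: change in each arm separately. A significant change in one arm and not in the other would not show that the arms differ.

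None gives a proportion. By contrast, the pain scores have both a continuous and a categorical model, each adjusted for the pre-operative value.

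**Would a yes/no endpoint be a good replacement?**

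Inputs: 19 per arm (SAP, Research Design) and a significance level of 0.05 (protocol 15.1, stated there for pain), taken as two-sided. The true proportions with persistent allodynia are not given, so a range is assumed. With p̄ = (p₁ + p₂)/2:

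power = Φ{ [|p₁ − p₂| − 1.96 √(p̄(1 − p̄) · 2/19)] / √[(p₁(1 − p₁) + p₂(1 − p₂))/19] }

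For p₁ = 0.70 and p₂ = 0.259: (0.441 − 1.96 × 0.162)/0.145 ≈ 0.85, so power is about 80%.

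| Assumed proportion, one arm | Proportion needed in the other for about 80% power |
|---|---|
| 0.90 | 0.495 |
| 0.70 | 0.259 |
| 0.50 | 0.096 |
| 0.30 | not reached (75% at 0.001) |

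Only differences of about 0.40 or more would be detected reliably. Force should stay continuous for the main comparison.

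**The case against.** The strongest reply is that the sentence need not mean what is feared. It can be parsed as incidence and severity of pain, plus mechanical allodynia as a separate item. The Statistical Method section fits that parse, since allodynia is handled only as a continuous force. Incidence may also be meant loosely, as how often something occurs; protocol 2.3 uses the word that way for pain. This stands as a real ambiguity. It does not remove the point: the phrase about following root canal treatment still applies to allodynia, and the visit is still unnamed.

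Three stronger readings are tempting, and the documents do not support them.

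- A reader might infer that nothing after treatment is observed at all. That is wrong: the visit 2 reading follows the randomised irrigation. Only the first days after visit 1 and the period after visit 2 are missing.
- A reader might infer that every patient has allodynia at entry by rule. No bite-force cut-off is an eligibility criterion, the diagnosis rests on percussion as well, and the inclusion criteria admit "a periapical diagnosis designated as symptomatic including symptomatic apical periodontitis, chronic apical abscess, acute apical abscess requiring root canal therapy". Allodynia at baseline is likely in nearly all patients, but not guaranteed.
- A reader might infer that mean force is biased by jaw strength or tooth type, because once a tooth stops hurting the reading reflects how hard the patient can bite. Under randomisation such differences add variance to the between-arm test, not systematic bias. The paired tests remove differences between patients.

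It is also fair to say that allodynia is not a protocol outcome, so the main pain question is untouched.

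**Conclusion.** The point holds as a mismatch between the stated aim and what is measured. The two readings support a between-arm comparison of the bite-force pain threshold 2-4 weeks after the first, randomised session. They do not support conclusions about new-onset allodynia, about the first 168 h (0 readings), or about completed root canal treatment (0 readings).

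This rests on two assumptions: that the SAP describes every bite-force reading taken, and that incidence is meant to cover allodynia, which is the natural reading but not the only one. If incidence covers pain alone, the new-onset part falls away, while the timing limit and the unnamed visit remain.

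The correction is worth making because it is nearly free and changes what may be claimed. It does not call the trial's pain results into question.

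**What to change.** In the SAP's Research Design section, drop incidence for allodynia. State the aim as change in, or persistence of, the bite-force pain threshold 2-4 weeks after the first treatment visit, before obturation.

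In Statistical Method, name visit 2 as the time point of the between-group bite-force comparison. Fit a linear model of the visit 2 treated-tooth reading on arm and the visit 1 treated-tooth reading, with the contralateral reading as a further covariate if wanted. Report the adjusted difference with a 95% CI. Keep the within-arm paired tests as description.

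A proportion with persistent allodynia, defined against the contralateral tooth, is optional and secondary. It should be added only if the cut-off is fixed before the data are examined. The documents give no cut-off, and the SAP is written in the past tense, so this may no longer be possible.

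Adjustment for days since visit 1 is not requested. The data list in protocol 5.2 does not include that interval, and section 16.1 removes date elements other than the year.

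Cost: a few lines of SAP text and one regression on readings already described, with no new measurement. The downside is a narrower allodynia claim.

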### **Inclusion criteria were:**

- (i) Patients who are 18 years of age or older
- (ii) Patients with premolar or molar with a pulpal diagnosis of necrotic pulp, symptomatic irreversible pulpitis, asymptomatic irreversible pulpitis and a periapical diagnosis designated as symptomatic including symptomatic apical periodontitis, chronic apical abscess, acute apical abscess requiring root canal therapy.
- (iii) teeth with fully formed apices
- (iv) teeth without internal or external resorption.

